13.4.2 Efficacy Analyses	66-67	Summary statistics including confidence interval for the treatment differences will be used to summary the results for the secondary endpoints. Testing will be performed for the key secondary responder rate endpoints. This testing will utilize a CMH test. The tests will be stratified by the randomization stratification factor. The time to first migraine analysis will be based upon Kaplan-Meier methods.	Summary statistics including confidence interval for the treatment differences will be used to summarize the results for the secondary endpoints. Testing will be performed for the key secondary endpoints and for the change in acute migraine medication days endpoint. For the key secondary endpoints (responder rates and percentage of subjects with a migraine on the day after dosing) this testing will utilize a CMH/extended CMH test. The tests will be stratified by the randomization stratification factor. The change in acute migraine medication day endpoints will be tested using an ANCOVA model similar to the one used for the primary	Provide additional information related to the new endpoints.

Section	Pg	Change From	Change To	Justification
			endpoints: change from baseline measure as the response, treatment and baseline acute migraine medication days as independent variables. The time to first migraine analysis will be descriptively summarized based upon Kaplan-Meier methods. The missing data rules provided in Section 13.3.2 will be used for the key secondary endpoints except for the percentage of subjects with a migraine (prevalence) on the day after dosing endpoint. Subjects who did not complete the diary on the day following dosing will be included in the prevalence rate calculation based upon their month 1 daily migraine rate. Hence, subjects with a migraine will be included in the rate calculation as a value of 1, subjects who completed the diary and did not have a migraine will be included as a zero and subjects who did not complete the diary will be included with a value between 0 and 1 equal to the number of month 1 migraine days / 28.	

16 References

- 1. "Effective Health Care Program, Migraine in Adults: Preventive Pharmacological Treatments, Executive Sumamry". Agency of Healthcare Research and Quality, Comparative Effective Review, AHRQ Pub. No. 13-EHC08-1-EF 2013; April
- 2. Preibisz. Calcitonin gene-related peptide and regulation of human cardiovascular homeostasis. Am J Hypertens. 1993; 6(5 Pt 1): 434-50.

1 CLINICAL TRIAL DESCRIPTION

According to the International Classification of Headache Disorder (ICHD)¹, migraine is a common disabling primary headache disorder manifesting in attacks lasting 4 to 72 hours. Migraine frequency is divided into episodic migraine and chronic migraine. Frequent Episodic migraine (FEM, 4 to 14 migraines days per month) affects approximately 17 percent of women and 6 percent of men.

Calcitonin gene-related peptide is a member of the calcitonin family of peptides and is thought to have a multiplicity of actions within the brain, including the facilitation of pain transmission and the induction of the nociceptive state, both of which may contribute to the mechanism of migraine^{2, 3}. ALD403 is a humanized anti- CGRP monoclonal antibody (anti-CGRP) that binds to CGRP and is being developed by Alder BioPharmaceuticals, Inc. for the prophylaxis of migraine.

1.1 Objectives

1.1.1 Primary Objective

The primary objective is:

• To evaluate the efficacy of repeat doses of ALD403 administered intravenous (IV) compared to placebo in subjects with FEM.

1.1.2 Secondary Objectives

The secondary objectives include the following:

- To evaluate the safety of repeat doses of ALD403 administered IV compared to placebo in subjects with FEM.
- To evaluate the pharmacokinetics (PK) and immunogenicity of repeat doses of ALD403 administered IV to subjects with FEM.

1.2 Clinical Trial Design

This phase 3, is a parallel group, double-blind, randomized, placebo-controlled trial of multiple infusions of ALD403 or placebo in subjects with FEM. Subjects who provide informed consent will be qualified based upon the inclusion and exclusion criteria and compliance with the eDiary. The key entry criteria are that the subject has FEM, which will be determined from the first 28 days of eDiary data following the screening visit. During this time the subject must experience \geq 4 and \leq 14 headache days of which at least 4 have to be migraine days and must have completed the eDiary at least 25 of the 28 days to be eligible.

The subject will be instructed to complete the eDiary daily from the screening visit through Week 48. Subjects will return to the site on Day 0 for randomization and first treatment, which should occur at least 29 days but no more than 35 days after the screening visit. Subject eligibility will be re-confirmed on Day 0, prior to randomization. Subjects will be randomized into one of three ALD403 dose levels (30 mg, 100 mg, and 300 mg) or placebo. Any subject found to be no longer eligible for the trial on Day 0, will not be randomized nor dosed. The subjects randomized and dosed will continue the study for 56 weeks. These 56 weeks are divided into two periods, i.e., a primary efficacy and safety period (Weeks 1-24) and a long term safety period (Weeks 25-56). Subjects will complete the eDiary daily through Week 48.

Approximately 800 subjects will be randomized and treated. Efficacy, safety, pharmacokinetic, and immunogenicity assessments will be conducted according to the Schedule of Events in Table 1.

Table 1: Schedule of Events and Assessment

			Pr	imary Ef	ficacy ar	nd Safety	Period		Lo	ng Term	Safety Per	riod
	Screen	Rand/	Wk 4	Wk8	Wk 12	Wk 16	Wk 20	Wk 24 ⁸	Wk 28	Wk 36	Wk 489	Wk 56
	D-35	$\mathbf{D0}$	D28 ±3	D56 ±3	D84 ±3	D112 ±3	$D140 \pm 3$	D168 +3	D196 ±7	$D252 \pm 3$	D336 +7	EOT/ET
Assessment	to -29	Tx			Tx			Tx		Tx		D392 + 7
Informed Consent	X											
In/Ex Criteria	X	X										
Demographics, Medical History, BDI-II	X											
Headache eDiary Review ¹	X	X	X	X	X	X	X	X	X	X	X	
Physical Exam Height and Weight ²	X	X						X		X		X
Brush Allodynia Test		X	X		X	X	X	X				
Vital Signs ³	X	X	X	X	X	X	X	X	X	X	X	X
C-SSRS ⁴	X	X	X	X	X	X	X	X	X	X	X	X
12-lead ECG ³	X	X	X	X	X			X	X	X	X	X
Hematology, Chemistry ⁵	X	X	X		X			X	X	X	X	X
HIV/Hepatitis B and C Urine Drug Screen	X											
Urine Preg (hCG) Test	X	X			X			X		X	X	X
Plasma ALD403 Serum Anti-ALD403 ⁶		X	X	X	X	X	X	X		X	X	X
SF-36		X	X	X	X	X	X	X		X		X
EQ-5D-5L, ASC-12		X	X	X	X	X	X	X				
AE and Con Meds Review	X	X	X	X	X	X	X	X	X	X	X	X
Randomization		X										
ALD403/placebo administration ⁷		X			X			X		X		

Abbreviations: TX: Treatment, Rand: Randomization, EOT/ET: End of Trial/Early Termination

¹Headache eDiary distributed at screening. eDiary review and compliance check through Week 48.

²Physical exam must be done pre-dose on Day 0, Week 24, 36. Height and Weight on Screening visit. Weight only on Day 0, Weeks 24, 36, 56

³Vital signs, 12-lead ECG pre-dose and 4 hours post-dose (± 30 minutes) on Day 0 and Weeks 12, 24 and 36

⁴C-SSRS Baseline/Screening Version at screening, C-SSRS Since Last Visit Version Day 0 (pre-dose), Weeks 4, 8, 12, 16, 20, 24, 28, 36, 48 and 56

⁵All blood draws obtained pre-dose on dosing days

⁶Sample for Plasma Free ALD403 and anti-ALD403 antibody drawn pre-dose on dosing days (within 1 hour prior to dosing)

⁷ Subjects must be monitored for at least 4 hours after the dosing completion.

⁸Week 24 must be done on the target day or 3 days after. Three days earlier than target date is not allowed.

⁹Week 48 must be done on the target day or seven days after. Seven days earlier than target date is not allowed.

1.3 Method of Assigning Subjects to Treatment Groups

Randomization will occur 29 to 35 days after the screening visit when the eligibility assessments are completed and eligibility verified. Sites will complete the randomization using an Interactive Web Response System (IWRS) and the randomization assignment will be obtained by the clinical trial site's unblinded pharmacist or Investigational Product consignee. Subjects will be randomized in equal ratios to one of the four 4 treatment groups (30 mg, 100 mg, or 300 mg of ALD403 or Placebo). Stratified permuted block randomization will be used. Stratification will be by migraine days during the screening period (≤9 days vs. >9 days).

Randomized subjects who terminate their clinical trial participation for any reason, regardless of whether Investigational Product was taken or not, will retain their randomization assignment and subject number.

1.4 Blinding

This clinical trial is double-blind, meaning the subjects and site personnel are blinded to treatment assignment, except for the clinical trial site's unblinded pharmacist or Investigational Product consignee. Immediately prior to PK/immunogenicity sample analysis, the bioanalytical laboratory will be unblinded in order to obtain the treatment assignments. Selected sponsor personnel in the Safety and Regulatory groups may be unblinded to individual subject's treatment assignments as required for safety reporting. More details can be found in the blinding plan. The study will remain blinded until the last subject has completed the Week 24 visit at which time the sponsor will be unblinded.

1.5 Sample Size

The planned sample size for this trial is 800 randomized and treated subjects. These subjects will be allocated into 4 treatment groups in a 1:1:1:1 ratio. Pair-wise testing of each ALD403 group vs. placebo will be performed. Two hundred subjects per group provides at least 95% power for each change in frequency of migraine days (Weeks 1-12) test individually assuming a treatment effect of at least 1 day and a common standard deviation of 2.7 days or less. Ninety percent power is retained for standard deviations up to 3 days. For the key secondary 75% responder

rates endpoints 95% power is achieved for the pair-wise comparisons assuming rates of 24% for placebo and 42% for ALD403. For the 50% responder rate endpoints 95% power is achieved for the pair-wise comparisons assuming rates of 50% for placebo and 68% for ALD403. For the percentage of subjects with a migraine on the day after dosing endpoint, 95% power is achieved for pair-wise comparisons assuming rates of 15% for placebo and 4% for ALD403.

These sample size calculations have been performed using Pass 2008 and are based upon t-tests and Chi-squared tests that should approximate the ANCOVA and CMH tests, respectively.⁴

2 STATISTICAL METHODS

2.1 Populations Analyzed

The analysis populations are defined as the following:

- Full Analysis Population Randomized subjects who received Investigational
 Product/placebo. Subjects will be summarized within the treatment group to which they
 were randomized. This population will be used for efficacy analyses.
- Safety Population Includes all subjects who received Investigational Product/placebo.
 Subjects will be summarized within the treatment group for which they actually received treatment. If a subject is treated with two different doses they will be summarized in treatment arm of the highest dose received. This population will be used for the safety analyses.
- PK Population All subjects who have at least one reportable plasma concentration. The PK population will be used for PK analyses.

2.2 Clinical Trial Endpoints

The efficacy, safety, pharmacokinetic and immunogenicity of ALD403 will be assessed using the following endpoints. Greater detail concerning these endpoints can be found in Section 2.2.2.

Primary Efficacy Endpoint

• Change in frequency of migraine days (Weeks 1-12)

Key Secondary Efficacy Endpoints

- 75% migraine responder rate (Weeks 1-4)
- 75% migraine responder rate (Weeks 1-12)
- 50% migraine responder rate (Weeks 1-12)
- Percentage of subjects with a migraine on the day after dosing

Other Secondary Efficacy Endpoints

- Change in acute migraine medication days (Weeks 1-12)
- Headaches/Migraines with acute medication usage
- 100% migraine responder rates (Weeks 1-12)
- Short-Form Health Survey (SF-36 v 2.0)
- Health-Related Quality of Life (EQ-5D-5L)
- Allodynia Symptom Checklist-12 (ASC-12)
- Brush (dynamic mechanical) Allodynia
- Migraine responder rates for time periods other than Weeks 1-12
- Change in frequency of migraine days between baseline and time periods other than Weeks 1-12
- Headache responder rates
- Change in the frequency of headache days
- Percent change in headache/migraine days
- Time to first migraine after dosing
- Headache/Migraine hours
- Headache/migraines with severe intensity

Tertiary Endpoints

• Headache episodes/migraine attacks

Exploratory Endpoints

- Headache/Migraine characteristics
- Headaches/Migraines with type of acute medication usage
- Headache episode/Migraine attack average length

Safety Endpoints

- Adverse events (AEs) and serious adverse events (SAEs)
- Changes in clinical laboratory assessments
- Vital Signs
- ECGs
- Suicidal ideation and behavior as measured by the Columbia-Suicide Severity Rating Scale (C-SSRS)

Pharmacokinetic Endpoints

• Free ALD403 plasma concentrations

Immunogenicity Endpoints

- Development of specific anti-ALD403 antibodies
- Characterization of specific anti-ALD403 antibodies for neutralizing activity

2.2.1 eDiary

Subjects will complete a daily headache eDiary from the time of screening to Week 48. The diary is to be completed each trial day whether or not the subject had a headache. These daily entries record if the subject took acute migraine medication on that day.

The eDiary data from the 28 days following screening visit will be used to determine eligibility criteria, and the baseline migraine and headache results.

2.2.2 Migraine and Headache Endpoints

In the statistical analysis plan the term headache will encompass both headaches and migraine headaches. Migraine headaches (migraines) are a subgroup of the headaches with the characteristics outlined below. In this way all migraines are headaches but not all headaches are migraines. Migraine and headache data will be collected through week 48. Headache episodes will be self-reported by the subject. An episode is a single headache event which lasts at least 30 minutes, as defined by the subject reported start and end time. The migraine and headache endpoints will be summarized in four week, twelve week and the twenty-four week intervals. Specifically, migraine and headache endpoints will be summarized for the four week intervals: Weeks 1-4, 5-8, 9-12, 13-16, 17-20, 21-24, ... 44-48, the twelve week intervals 1-12, 13-24, 25-36, 37-48, and Weeks 1-24, 25-48 as outlined in Section 2.3. The results from Weeks 1 to 12 will be used for the primary analysis.

For this trial, migraines are defined using the definition of migraine without aura and probable migraine without aura as outlined by the International Headache Society. These definitions do not take the presence of aura into account. Subjects will report if they experienced aura with their headache. Hence, in the rare case of aura that does not develop into a migraine, this will not be classified as a migraine but a headache that meets the definition of a migraine without aura will be considered a migraine regardless of if aura was present or not.

Migraine Day

A migraine day is defined as any day with a headache that meets the migraine or probable migraine characteristics as outlined in the International Headache Society (IHS), ICHD II 2004-II, Section 1.1 and 1.6. Specifically, a migraine is defined as a self-reported headache that:

- 1. Lasted 4-72 hours
- 2. Had at least 2 of the following
 - a. Unilateral location
 - b. Pulsating quality
 - c. Moderate or severe pain intensity
 - d. Aggravation by or causing avoidance of routine physical activity

3. Had at least 1 of the following

- a. Nausea and/or vomiting
- b. Photophobia and phonophobia

A probable migraine is a headache that meets only 2 of the above criteria. These characteristics will be summarized for each 4-week interval.

Frequency, Change and Percent Change of Migraine Days / Headache Days

The frequency of migraine days is the number of migraine days within four week intervals and the average four week frequency in twelve and twenty-four week intervals. Change from baseline is the difference in frequency between baseline and the counts within these four week intervals. The 12 and 24 week change is the difference in the frequency between baseline and the average of the, 4 week intervals. The percent change is 100 times the ratio of the change and the baseline frequency. Similar measures will be produced based upon headache frequency.

Migraine/ Headache Responder Rate

Three responder rates will be utilized: 50%, 75% and 100%. A responder is a subject who achieves a \geq 50% reduction, \geq 75% reduction, or 100% reduction in migraine days, respectively. These reductions will be evaluated by comparing the baseline frequency of migraine days to the migraine frequency in four week intervals.

Results from the four week intervals will be averaged to produce 12 and 24 week responder endpoints. A responder will be a subject who achieves the specified percent reduction in migraine headache days when response rates for each of the four week intervals are averaged.

Migraine Hours / Headache Hours

Migraine hours are the sum of the duration of migraines within four week intervals, and the average four week duration within 12 and 24 week intervals. Headache hours are similarly defined but include all headaches. Subjects with no migraines/headaches will have a duration of zero.

Migraine Attack / Headache Episode

A migraine attack is defined as 1 continuously recorded migraine. One attack may result in multiple migraine days. Headache episodes are similarly defined.

Migraine / Headache Severity

Headache severity will be collected on a 3 point scale: mild pain, moderate pain, severe pain. The percent of migraines and headaches with severe pain will be summarized. Subjects with no migraines/headaches will be included with a rate of zero.

Acute Medication Usage

The percent of migraines and headaches with acute medication usage as recorded in the eDiary will be summarized. Subjects with no migraines/headaches will be included with a rate of zero.

Acute Migraine Medication Usage

The number of days within 4 week intervals that subjects used acute migraine medication (i.e. triptan or ergotamine) will be summarized in 4, 12 and 24 week intervals. The 12 and 24 week results will be the average of the individual 4 week results that make up those wider intervals (e.g. the secondary endpoint of Weeks 1-12 will be the average of the Weeks 1-4, 5-8 and 9-12 results). The change from baseline for these measures will be the difference between the baseline and post baseline interval.

Percentage of subjects with a migraine on the day after dosing

The percent of subjects with a migraine on the day after first dose will be summarized.

eDiary Reported Medication Usage

The percent of days per 28 days with medication usage will be summarized overall and by the type of medication used.

Average Migraine / Headache Length

The length of each migraine attack is the average of the duration of each migraine attack within a four week intervals. Headache hours are similarly defined but include all headaches. Subjects with no migraines/headaches will have a duration of zero.

Time to First Migraine

Time to the first migraine after dosing will be analyzed based upon the migraine data entered into the eDiary.

2.2.3 SF-36 Health Survey (SF-36 v2.0)

The SF-36 v2.0 is a health survey containing 36 questions consisting of eight scaled scores to measure quality of life over the past 4 weeks. The eight sections measured are vitality, physical functioning, bodily pain, general health perceptions, physical role functioning, emotional role functioning, social role functioning, and mental health.

2.2.4 EQ-5D-5L

The EQ-5D-5L is a descriptive system of health-related quality of life states consisting of five dimensions/questions (mobility, self-care, usual activities, pain/discomfort, anxiety/depression) each of which can take one of five responses. The responses record five levels of severity (no problems/slight problems/moderate problems/severe problems/extreme problems) within a particular EQ-5D dimension. The EQ-5D-5L additionally includes a VAS scale. Each item will be summarized separately.

2.2.5 Allodynia Symptom Checklist (ASC-12)

The ASC-12 includes 12 questions about the frequency of various allodynia symptoms in association with headache attacks. For individuals with more than one type of headache, questions are directed to the "most severe type of headache." Each item is measured on a Likert type scale option with response categories: "Does not apply to me", "never," "rarely," "less than half the time," and "half the time or more". ASC items were scored as 0 (i.e., never, rarely, or does not apply to me), 1 (less than half the time), and 2 (half the time or more), yielding scores that ranged from 0 to 24. In this trial if a single item is missing it will be scored as a zero. If

more than one item is missing the total score will be missing. The interpretation of the total score is provided below.

Score Range	Allodynia
0-2	None
3-5	Mild
6-8	Moderate
≥9	Severe

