The EQ-5D-5L is a descriptive system of health-related quality of life states consisting of five dimensions/questions (mobility, self-care, usual activities, pain/discomfort, anxiety/depression) each of which can take one of five responses. The responses record five levels of severity (no problems/slight problems/moderate problems/severe problems/extreme problems) within a particular EQ-5D dimension. The EQ-5D-5L additionally includes a VAS scale. Each item will be summarized separately.

Allodynia Symptom Checklist (ASC-12)

The ASC-12 includes 12 questions about the frequency of various allodynia symptoms in association with headache attacks. For individuals with more than one type of headache, questions are directed to the "most severe type of headache." Each item is measured on a Likert type scale option with response categories: "Does not apply to me", "never," "rarely," "less than half the time," and "half the time or more," see Appendix 15.5. ASC items were scored as 0 (i.e., never, rarely, or does not apply to me), 1 (less than half the time), and 2 (half the time or more), yielding scores that ranged from 0 to 24. In this study, if a single item is missing it will be scored as a zero. If more than one item is missing the total score will be missing. The interpretation of the total score is provided below.

Score Range	Allodynia
0-2	None
3-5	Mild
6-8	Moderate
≥9	Severe

Brush Allodynia

Dynamic mechanical brush allodynia will be tested by lightly brushing a 10 by 10 cm gauze pad bilaterally, 1-2 cm over each eyebrow at a rate of 2/second, for a total of 10 times. ¹⁴ For each side of their forehead, subjects will be asked to assess the degree of pain elicited by the gauze on a scale of 0 to 10 with 0 being no pain and 10 being the worst imaginable pain. ¹⁵

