14.4 Data Collection and Electronic Data Capture (EDC)

The data collected during the study (except clinical laboratory test results, ECG results, PK analyses, Immunogenicity) will be recorded in the subject's electronic CRF. The Short-Form Health Survey (SF-36), Health related Quality of Life (EQ-5D-5L), Allodynia Symptom Checklist-12 (ASC-12) and C-SSRS will be completed on paper forms and then entered into the EDC system. The study site(s) will use an EDC system that is compliant with relevant Food and Drug Administration (FDA) regulatory requirements per 21 CFR Part 11. Data queries and data corrections will be handled through the same system. All transactions within the EDC system are fully documented within an electronic audit trail. Each set of completed CRFs must be reviewed after being source verified by monitor and electronically signed and dated by the Investigator.

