15.5 Allodynia Symptom Checklist (ASC-12)

Allodynia Symptom Checklist (ASC-12)

Question: How often do you experience increased pain or an	Does not			Less than	Half the
unpleasant sensation on your skin during your most severe type of	apply to	Never	Rarely	half the	time or
headache when you engage each of the following?	me			time	more
	Score: 0	Score: 0	Score: 1	Score: 2	Score: 2
Combing your hair					
Pulling your hair back (e.g., ponytail)					
Shaving your face					
Wearing eyeglasses					
Wearing contact lenses					
Wearing earrings					
Wearing a necklace					
Wearing tight clothing					
Taking a shower (when shower water hits your face)					
Resting your face or head on a pillow					
Exposure to heat (e.g., cooking, washing your face with hot water)					
Exposure to cold (e.g., using an ice pack, washing your face with cold water)					
Total score					
Sum of total scores					

Allodynia	ASC range	
None	(0-2)	
Mild	(3-5)	
Moderate	(6-8)	
Severe	(9 or more)	

15.6 Change Table for Amendment 4

Section	Pg	Change From	Change To	Justification
Cover page	1			Change in Sponsor's Medical Monitor
Signature Page	2			Change in Sponsor's Medical Monitor
1 Protocol Synopsis - Clinical Trial Endpoints	5	 Key Secondary Endpoints 75% migraine responder rate (Weeks 1-4) 75% migraine responder rate (Weeks1-12) 	 Key Secondary Endpoints 75% migraine responder rate (Weeks 1-4) 75% migraine responder rate (Weeks 1-12) 50% migraine responder rate (Weeks 1-12) Percentage of subjects with a migraine on the day after dosing 	Inclusion of additional endpoints that are believed to be clinically meaningful and would provide additional support and understanding of ALD403's effectiveness in migraine prophylaxis.
	6	Other Secondary Endpoints Headache/migraines with acute medication usage 50% and 100% migraine responder rates (Weeks 1-12) Short-Form Health Survey (SF-36) Health-Related Quality of Life (EQ-5D-5L) Allodynia Symptom Checklist-12 (ASC-12) Brush (dynamic mechanical) Allodynia Migraine responder rates for time periods other than Weeks 1-12.	Other Secondary Endpoints Change in acute migraine medication days (Weeks 1-12) Headache/migraines with acute medication usage 100% migraine responder rates (Weeks 1-12) Short-Form Health Survey (SF-36) Health-Related Quality of Life (EQ-5D-5L) Allodynia Symptom Checklist-12 (ASC-12)	The change in acute migraine medication days endpoint has been added as requested by the FDA.

Section	Pg	Change From	Change To	Justification

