3.4.6 Other Secondary Efficacy Analyses

The secondary endpoints will be summarized with descriptive statistics by time point. These summary measures will be based upon the observed results and where appropriate the change from baseline results. The denominator for percentages will be the total number of assessments collected at each visit.

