3.4.6.3 Allodynia Symptom Checklist-12 (ASC-12)

The ASC-12 total score and change from baseline will be summarized using the Full Analysis Population at each scheduled visit by treatment group using descriptive statistics. In addition, allodynia severity will be summarized using frequency counts for each scheduled visit.

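### The ASC-12 form in Protocol Appendix 15.5 prints a different item-scoring key from Protocol 12.1.2 and SAP 2.2.5, so the same answers can give different totals and allodynia categories

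*SAP*

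**What the plan says.** Three places give a scoring key for the same five responses.

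- **SAP 2.2.5:** "ASC items were scored as 0 (i.e., never, rarely, or does not apply to me), 1 (less than half the time), and 2" for *half the time or more*.
- **Protocol 12.1.2** has the same key, beginning "ASC items were scored as 0 (i.e., never, rarely, or does not apply to me", and refers the reader to Appendix 15.5 for the form.
- **Protocol Appendix 15.5** prints the score row "Score: 0 Score: 0 Score: 1 Score: 2 Score: 2" under the columns *does not apply to me*, *never*, *rarely*, *less than half the time* and *half the time or more*, in that order. The form has a total row and a row labelled "Sum of total scores".

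The severity bands are the same in all three: None 0–2, Mild 3–5, Moderate 6–8, Severe 9 or more.

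On data capture, Protocol 14.4 says that "Allodynia Symptom Checklist-12 (ASC-12) and C-SSRS will be completed on paper forms and then entered into the EDC system". On analysis, SAP 3.4.6.3 says that "The ASC-12 total score and change from baseline will be summarized using the Full Analysis Population at each scheduled visit" by treatment group, and adds frequency counts of allodynia severity.

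**The concern.** The protocol contradicts itself, because its endpoint text points to a form that scores two of the five responses one point higher. The SAP follows the text. Nothing else in the plan would expose the difference, since both keys share the same maximum and the same cut-offs.

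What is at stake is the ASC-12 total, its change from baseline and the severity counts at each scheduled visit. If scores or totals written on the form reach the database, these outputs would not follow the SAP key. The difference need not cancel against baseline, because the form gives its top two frequency categories the same score and so cannot register a move between them.

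**Working it through.** **Inputs.** 12 items (SAP 2.2.5); form key 0, 0, 1, 2, 2 (Protocol Appendix 15.5); text key 0, 0, 0, 1, 2 (Protocol 12.1.2, SAP 2.2.5); the severity bands given above.

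**The plan's own figure.** SAP 2.2.5 gives a total from 0 to 24. Under either key the maximum is 12 × 2 = 24, so the stated range reproduces and cannot show which key is in use.

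**Formulas.** Let *r*, *l* and *h* be the numbers of items answered *rarely*, *less than half the time* and *half the time or more*.

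- SAP total = *l* + 2*h*
- Form total = *r* + 2*l* + 2*h*
- Form minus SAP = *r* + *l*, which runs from 0 to 12 and is never negative

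**Examples (all other items score 0).**

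| Answers | SAP total | Form total |
|---|---|---|
| 3 *rarely* | 0 (None) | 3 (Mild) |
| 2 *less than half the time* | 2 (None) | 4 (Mild) |
| 5 *less than half the time* | 5 (Mild) | 10 (Severe) |
| 9 *rarely* | 0 (None) | 9 (Severe) |
| 12 *less than half the time* | 12 (Severe) | 24 (Severe) |

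The last row shows that the category does not always move.

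**How general this is.** There are 455 combinations of (*r*, *l*, *h*) with *r* + *l* + *h* ≤ 12. The totals differ in 442 of them, that is, in all but the 13 with *r* = *l* = 0. The category differs in 210 (210/455 = 46%). These are counts of possible answer sets, not expected patient frequencies; the documents give no ASC-12 response distribution.

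**Change from baseline.** Suppose six items move from *half the time or more* to *less than half the time*.

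- SAP: 6 × 2 = 12 to 6 × 1 = 6, a change of −6 (Severe to Moderate).
- Form: 6 × 2 = 12 to 6 × 2 = 12, a change of 0 (Severe at both visits).

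**Can the SAP key be rebuilt from stored form scores?** A stored 0 or 1 always converts to 0 under the SAP. A stored 2 may be either of two responses, which the SAP scores 1 and 2. Five items stored as 2, with the rest 0, could be any SAP total from 5 × 1 = 5 (Mild) to 5 × 2 = 10 (Severe). It cannot be rebuilt from EDC alone.

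**Could the mismatch come from reading the table?** A shifted column cannot explain it: the values {0, 0, 1, 2, 2} and {0, 0, 0, 1, 2} differ in any order. A misread digit cannot be fully excluded without the original page.

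**The case against.** The strongest case is that the analysis rule is already clear. The protocol text and the SAP both score by named response and agree with each other; the outlier is a score row on an appended form. The SAP's missing-item rule (one missing item counts as zero, more than one makes the total missing) implies item-level data, which makes use of the handwritten total unlikely. Harm then requires EDC to store printed scores instead of responses, and no document says so. The endpoint is one of 15 other secondary endpoints, covered by the SAP 3.4.6 statement that "The secondary endpoints will be summarized with descriptive statistics by time point". All arms would use the same form, so no built-in bias in favour of ALD403 is shown.

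Most of this stands, and it limits the consequence. It does not remove the contradiction or close the route into the data. Item-level data could still mean the printed item scores, and the paper form invites a site to enter those or the total.

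It is also fair that the documents do not contain the instrument's source scoring, and that the near-identical protocol and SAP wording is not two independent confirmations. The documents therefore show that form-based scores would depart from the SAP key. They do not by themselves prove which key belongs to the instrument.

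**Conclusion.** The concern holds. The form and the text give different scores to two of five responses, and the form total exceeds the SAP total by the number of those answers, up to 12 points on a 24-point scale. That can move a subject from None to Severe, or hide a six-point improvement.

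Whether the reported results are affected depends on one fact that the documents do not give, namely what EDC holds for each item:

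- **Response categories, scored by the SAP key:** no effect on the analysis.
- **Printed item scores or form totals:** the totals, changes and severity counts in SAP 3.4.6.3 would not follow the SAP key.

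The primary and key secondary tests are unaffected either way, because ASC-12 is outside the serial procedure in SAP 2.7.5. This should be corrected, but it does not threaten the trial's main conclusions. The mismatch itself rests on the printed digits in Appendix 15.5 having been read correctly.

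**What to change.** 1. Reconcile the three places to one key. Protocol 12.1.2 and SAP 2.2.5 already agree, so the direct correction is to the Appendix 15.5 score row, after a check of the original page and of the instrument's source scoring.
2. Confirm from the EDC field definition what was captured for each ASC-12 item.
3. Add to SAP 2.2.5: *The ASC-12 total is derived by program from the recorded response category for each item, using the key above; scores or totals written on the form are not used.*

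The cost is one corrected row, one SAP sentence and one database check. If EDC holds response categories, nothing more is needed. If it holds printed item scores, the items stored as 2 must be re-read from the paper forms and the items stored as 1 recoded to 0. ASC-12 is scheduled at seven visits (Day 0 and Weeks 4, 8, 12, 16, 20 and 24), so the upper limit is 800 × 7 = 5,600 forms, less those with no item scored 2. If only totals were stored, the item responses must be entered from the paper forms.
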